5.4.3 Parameters to be monitored

The following progress will be monitored throughout the course of the research to ensure the safety of subjects as well as the integrity and confidentiality of their data.

- An evaluation of the progress of the research study, including subject recruitment and retention, and an assessment of the timeliness and quality of the data.
- A review of collected data (including adverse events, unanticipated problems, and subject withdrawals) to determine whether there is a change to the anticipated benefit-to-risk assessment of study participation and whether the study should continue as originally designed, should be changed, or should be terminated.
- An assessment of external factors or relevant information (e.g., pertinent scientific literature reports or therapeutic development, results of related studies) that may have an impact on the safety and study participants or the ethics of the research study.
- A review of study procedures designed to protect the privacy of the research subjects and the confidentiality of their research data.

The severity of adverse changes in physical signs or symptoms will be classified as follows:

- Grade 1 (Mild): asymptomatic or mild symptoms; clinical or diagnostic observation only; intervention not indicated.
- Grade 2 (Moderate): minimal, local or noninvasive intervention indicated; limiting age-appropriate ADL (Activities of Daily Living).
- Grade 3 (Severe): medically significant but not immediately life-threatening; hospitalization or prolongation of hospitalization indicated; disabling; limiting self care ADL.
- Grade 4 (Life-threatening): consequences; urgent intervention indicated.
- Grade 5 (Death): event is a direct cause of death.

5.4.4 Frequency of Monitoring

The Investigator will review subject safety data as it is generated. The Investigator, sub-investigators, and the research staff will meet on a two week interval to re-evaluate study goals, subject recruitment, data coding and retention, documentation and identification of adverse events, complaints and confidentiality of subjects. There will be an evaluation of the progress of the research study, including assessments of data quality, time lines, participant recruitment, accrual, and retention. The Investigator will also review the outcome and adverse event data to determine whether there is any change to the anticipated benefit-to-risk ratio of study participation and whether the study should continue as originally designed or should it be re-evaluated and changed.

5.4.5 Reportable Adverse Events

For this study, a serious adverse event is any untoward clinical event that is thought by the investigator to be study-related, that is also:

1. Fatal or immediately life threatening
2. Permanently disabling, or severely incapacitating.
3. Requires or prolongs inpatient hospitalization.
4. Important medical events that may not result in death, be life threatening, or require hospitalization may be considered serious adverse events when, based upon appropriate medical judgment, they may jeopardize the patient, or subject, and may require medical, or surgical intervention to prevent one of the serious outcomes listed above.

If clinically important and unexpected adverse experiences, or clinically important study-related adverse experiences occur, they will be recorded on the adverse event case report form.

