Data Monitoring Plan. Data will be collected using standardized forms and will only be identified using the participant's ID number (no names or identifying information will be on the forms). The codes that link the names of participants and their ID numbers will be kept confidential by the PI located on a password protected document on a secured drive. These data will only be accessible to the PI and staff working directly with data with the study. All data will be entered on-line, by the project coordinator. Data will be double entered in the computer independently by trained study staff, and data entry discrepancies will be monitored and corrected by the project coordinator, based on source documents. The quality of the data will be monitored on an ongoing basis. Data

quality will be monitored by inspection of the completed forms by the study coordinator and any problems detected will be discussed with the PIs.

In the proposed study we will use the following University of Pittsburgh IRB definition of reportable events for the reporting of adverse events.

1. Internal Adverse Events that are (i) Unexpected, (ii) Related or Possibly Related to the Research Intervention, and (iii) serious or otherwise suggests that the research places the subject or others at a greater risk of harm (including physical, psychological, economic or social harm) than was previously known or recognized.
2. External Adverse Events that are (i) Unexpected; (ii) Related to the Research Intervention and (iii) Serious or otherwise suggests that the research places subjects or others at greater risk than was previously recognized

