Any event meeting #1 or #2 above will be reported immediately to the IRB in their required format. In the event that a participant either withdraws from the study or the PIs decide to discontinue a participant due to a SAE, the participant will be monitored by the co-PIs until (a) a resolution is reached (e.g., the problem has resolved or stabilized with no further change expected), (b) the SAE is determined to be clearly unrelated to the study intervention, or (c) the SAE results in death. Outcomes of SAEs will be regularly reported to the IRB. A summary of the SAEs that occurred during the previous year will be included in the annual progress report as well as in the annual IRB renewal. Suicidal ideation and AEs will be formally assessed immediately after treatment and referrals for further care will be made as needed. In the Informed Consent Form, we will provide specific information about emergency contacts. Participants are instructed to contact [name] during working hours. After hours participants will be provided the information on how to contact the cardiology fellow on call.

Stopping Rule:

For safety reasons, we propose to discontinue participation for any subject who experiences *any of the following*:

1. Methemoglobin greater than 5% after dose lowering
A nitrite dose reduction is proposed from 40 mg three times daily to 20 mg three times daily if this methemoglobin % is reached at any study interim visit, as described in section 2.2.6 (phone report of change in skin tone and dizziness or other symptom suggestive of methemoglobinemia). Follow up symptom assessment for 48 hours and repeat methemoglobin in 3 days will be implemented. If methemoglobin is greater than 5% on the lower nitrite dose, participation in the study for the subject will be discontinued.
2. Blood pressure drop after dose lowering
Blood pressure and related symptoms.

If subjects experience lightheadedness or dizziness after visit 3 while they are on the drug, we request that they call the study coordinator who will inventory their symptoms, compare to baseline (measured at pK) levels, and discuss need for interim visit with study physician. If a visit is indicated, we will measure blood pressure, RR, heart rate, and check methemoglobin level by a finger probe. A study physician will evaluate each subject, including:

- a. review of all clinical measures,
- b. subject history of symptoms,

c. blood pressures pre- and while on drug.

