5.4.6 Adverse Events Reporting Timeline

Life-threatening or fatal unexpected adverse events associated with the use of the study drug or procedures must be reported to the IRB within 24 hours of discovery of the incident with subsequent follow-up submission of a detailed written report.

The FDA must be notified by telephone or facsimile transmission of a human adverse event that is fatal or life-threatening no later than 7 calendar days after receiving the respective human adverse event information, followed by the subsequent submission of a written IND Safety Report.

Serious and unexpected adverse events associated with the use of the study drug or procedures must be reported to the IRB with subsequent follow-up submission of a detailed written report in accordance with the respective policies and procedures of the IRB. Written IND Safety Reports will be submitted to the FDA as soon as possible and, in no event, later than 15 calendar days following the investigator-sponsor's receipt of the respective adverse event information.

A summary report of the findings will be prepared and submitted to the regulatory agencies.

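### Section 5.4.5 builds the investigator's view of relatedness into the SAE definition, so serious events judged unrelated are not SAEs and, if that definition governs, are left out of the SAE reports and annual summary

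*Combined protocol and SAP*

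**What the plan says.** Section 5.4.5 gives the only definition of an SAE in the protocol, and it is worded to apply to the whole study: "a serious adverse event is any untoward clinical event that is thought by the investigator to be study-related", provided that the event also meets one of four listed outcomes. In short, these are death or immediate threat to life, permanent disability or severe incapacity, hospital admission or a longer stay, and other medically important events. The two conditions are joined, so both must hold.

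The same section sets the rule for the case report form: "If clinically important and unexpected adverse experiences, or clinically important study-related adverse experiences occur, they will be recorded" there.

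Other sections use the term or the idea as follows.

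- Section 5.4.1, on participants who leave the study because of an SAE, lists as one end of follow-up that "the SAE is determined to be clearly unrelated to the study intervention".
- The same section promises two outputs: "Outcomes of SAEs will be regularly reported to the IRB", and "A summary of the SAEs that occurred during the previous year will be included in the annual progress report" and in the annual IRB renewal.
- Section 5.4.1 also adopts the University IRB's definition of a reportable event. For internal events this lists unexpectedness, relatedness ("Related or Possibly Related to the Research Intervention") and seriousness as separate criteria.
- Section 5.4.6 says "Serious and unexpected adverse events associated with the use of the study drug or procedures must be reported to the IRB". On fatal and life-threatening events it says "The FDA must be notified by telephone or facsimile transmission of a human adverse event that is fatal or life-threatening", with no condition on relatedness in that sentence.

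**The concern.** Seriousness describes the outcome of an event. Relatedness is a judgement about its cause. When the second is made part of the first, one person's causal judgement decides whether a serious event exists in the SAE count at all, and a reader of the count cannot see what was set aside.

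The synopsis (Study Design) names safety as something the study aims to assess. Section 2.1 describes an open-label, non-randomized study, and section 2.2 gives nitrite to the whole study population, controls included. No untreated group exists against which a run of events judged unrelated could be compared. In subjects aged 70 or older, many of them with heart failure, an admission may plausibly be put down either to the drug or to the underlying disease. At stake is whether the SAE outcome reports and the annual summary show every serious event or only those attributed to the study.

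**Working it through.** No power or sample size figure is involved. The check is a comparison of the text.

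**Step 1: the two possible SAE sets.** Let S be the events that meet one of the four outcomes, and R the events that the investigator thinks are related.

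- Section 5.4.5: SAE = S and R.
- Seriousness judged separately from cause: SAE = S.
- Difference: S and not R, that is, serious events judged unrelated.

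**Step 2: which reading the other sections support.**

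| Place | Use | Fit with 5.4.5 |
|---|---|---|
| 5.4.1, end of follow-up | An SAE may prove unrelated | In tension; possible only if first judged related and later changed |
| 5.4.1, IRB reportable events | Relatedness and seriousness listed separately | Relatedness is redundant where the event is serious; no contradiction |
| 5.4.6, serious and unexpected events | Association with drug or procedures added to serious | Redundant; no contradiction |
| 5.4.6, FDA telephone or facsimile notice | Fatal or life-threatening, no relatedness condition | Does not use the term SAE; unaffected |

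No section says which sense applies to the outcome reports or the annual summary.

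**Step 3: what depends on the choice.** Both outputs in 5.4.1 are defined in terms of SAEs. Under 5.4.5 they contain S and R only. If N is the number of serious events and p the share judged related, the reported number is N × p and the shortfall is N × (1 − p). The shortfall runs from none (p = 1) to all N (p = 0). The documents give neither N nor p, so no narrower figure can be defended.

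**Step 4: the form rule in 5.4.5, for clinically important events.**

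| | Judged related | Judged unrelated |
|---|---|---|
| Unexpected | Recorded | Recorded |
| Expected | Recorded | No stated route |

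Three of the four cells are covered. The gap is the fourth.

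**Step 5: routes that do not depend on the SAE label.**

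- Section 5.4.1: staff report all adverse events to a PI, who reports them to the IRB.
- Table 1: adverse events are assessed at Visit 3, the four weekly calls, Visits 4 and 5 and the follow-up call.
- Section 5.4.3: severity is graded, including admission, threat to life and death, with no relatedness condition.
- Sections 5.4.3 and 5.4.4: the benefit-risk review covers adverse event data generally.

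**The case against.** The strongest reply is that little is lost. Serious events judged unrelated are still collected, graded, passed to a PI and, on the face of 5.4.1, sent on to the IRB. The IRB definition quoted later in that section may narrow this last route, but it does not remove the others. For the serious, unexpected and related events that go to the IRB on an expedited basis, the two senses of SAE give largely the same set. This stands, and it limits the point to the label, the count and the fourth cell of the form rule.

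Four stronger readings are tempting, and the documents do not support them.

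- *Unrelated serious events go uncaptured or unreported.* The routes in the last step of the working contradict this.
- *Section 5.4.5 contradicts 5.4.1 and 5.4.6 outright.* The relatedness wording in the IRB definition and in 5.4.6 is at most redundant. The follow-up clause in 5.4.1 is in real tension, but it can be read as a later change of judgement.
- *The investigator's judgement is unreliable because nobody is untreated.* Individual causality is a clinical judgement in any design. What can be said is that it cannot be checked against an untreated group here.
- *One relabelled event changes a trial result.* No SAE proportion is an endpoint (section 2.4) or a planned analysis (section 2.5), so there is no planned estimate to move.

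The form gap is also narrow. Hypotension in heart failure subjects is expected because section 5.1.1 lists it as a risk of the drug, which makes it an unlikely candidate for a judgement of unrelated. The documents show no event that plainly falls in the gap.

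**Conclusion.** The point holds in a limited form. As worded, 5.4.5 excludes serious events judged unrelated from the SAE category. If that definition governs the outputs in 5.4.1, the outcome reports and annual summary give an incomplete count of serious events. The conclusion is conditional on that reading, which the documents do not settle, although 5.4.5 is the only definition offered. The size of the undercount is unknown. Nothing here affects the efficacy analyses or the wording of the FDA notice. It is worth correcting because safety is a stated aim, attribution has no untreated comparison, and the correction is small.

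**What to change.** 1. In 5.4.5, delete the clause that requires the investigator to think the event study-related, and define a serious event by the four listed outcomes alone.
2. Record all adverse events on the case report form, with relatedness and expectedness as two separate fields. This closes the gap for events that are expected and judged unrelated.
3. In 5.4.1, state that the SAE outcome reports and the annual summary cover all serious events whatever their judged cause.
4. Keep relatedness only as a criterion for expedited reporting. Leave the reportable-event definition in 5.4.1 as it is, because it is the University IRB's own, and check 5.4.6 for consistency with the revised 5.4.5.

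The cost is one deleted clause, a sentence on the scope of the SAE reports and summary, a revised recording rule and two form fields. The downside is slightly more event recording and possibly a higher reported SAE count, which the relatedness field would let a reader interpret.

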
Study Design:
	
The study aims to assess the safety and feasibility of oral nitrite in adults with HFrEF, HFpEF or healthy control.
 
Subjects who meet the Inclusion Criteria and none of the Exclusion Criteria will receive oral sodium nitrite for 4 weeks. We will stratify dosing as below:
 
Study drug to be initiated and prescribed as below:
 
 a. 20 mg tid to subjects who 
 i. are \geq80 years of age or, ii. are age 70 to <80 years with recent history of low blood pressure or other factors that PI judges to be at higher risk for hypotensive response b. 40 mg tid to subjects who 
 i. are age 70 to <80 with no recent history of low blood pressures or PI judges to be at lower risk for hypotensive response c. Subjects to ingest drug once in the morning and again in the early afternoon and again in the evening, approximately 6 hours apart.

	
Subjects will be evaluated as outpatients with the first dose of study drug. Blood pressure, heart rate, methemoglobin levels and plasma nitrite will be measured in the first two hours after dosing. Every week safety visits will occur by phone to assess symptoms, adverse events (AE), interval histories and medication compliance review.
 
Subjects will also be contacted by the study investigator and/or the study coordinator by phone for a follow-up assessment one week following completion of Visit 5.

Planned Sample Size:	30 subjects
Duration of Treatment:	4 weeks

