2.2 DETAILED DESCRIPTION OF STUDY DESIGN

Subjects will undergo a screening visit to determine that eligibility requirements are met. Prior to receiving the study drug, subjects will be scheduled within 4 weeks of screening for a baseline assessment.

Subjects who meet the Inclusion Criteria and none of the Exclusion Criteria will be provided study drug. The study population ($n=30$) will receive oral sodium nitrite combination for 4 weeks:

Drug: oral formulation of sodium nitrite 20 or 40 mg oral three times daily or TID (once in the morning and again in the early afternoon and again in the evening)

Subjects will complete a 4-week outpatient treatment period. During the treatment period, subjects will be evaluated at weekly intervals. Throughout the study period, subjects will be asked to remain diligent in recording the time of study drug dosing and any associated symptoms (diary cards will be pre-dated).

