2.2.3. Treatment Period

Subjects will undergo study treatment duration of 4 weeks of 14N sodium nitrite 20-40 mg three times daily. This is considered appropriate to study benefits of oral nitrite therapy to improve physical function in patients with HFrEF and HFpEF and age-matched controls.

2.2.4. Safety Monitoring:

Subjects will be contacted by phone weekly and this will include symptom review, assessing adverse events, interval histories and medication compliance.

In addition to these phone evaluations, subjects will be encouraged to immediately contact the study investigator and/or the study coordinator with questions, concerns, or to report new symptoms that occur during their study participation. If there are particular concerns that need to be addressed the subject will be asked to return to the EMRC or SMART Center as soon as possible for evaluation. Evaluations will be planned on an individual basis (depending on each individual's circumstances) and may include weight, vital signs, methemoglobin %, medication compliance review, and assessment by the study physician. If appropriate, based upon the evaluation, medical treatments will be provided to subjects, including appropriate referral to physicians or other services at the UPMC.

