5.4 DATA SAFETY MONITORING PLAN

5.4.1 Data Safety Monitoring Plan

Monitoring of safety and data quality in the proposed study will be the responsibility of all personnel on the project, with primary responsibility and supervision by the PI. Both the Institutional Review Board will approve the Statement of Informed Consent for the study and provide institutional oversight of data and safety issues. The study protocol will be approved prior to recruiting or consenting any participants. Moreover, the study will be reviewed on an annual basis by the IRB committee. Each participant will sign the Informed Consent Form described above prior to participating in the study. To ensure participant safety, once participants are enrolled in the study, study staff will immediately report all adverse and serious adverse events to one of the PIs. The PI will, per standardized procedures, report them to the IRB for their review. With regard to monitoring of data quality and protected health information, all required personnel proposed for this project will have the required human subjects and confidentiality training, which includes information about maintaining data integrity and security. Confidentiality will be guarded using established procedures such as storing data in locked cabinets within locked offices or locked data rooms, coding by study identification numbers rather than any personally identifying information to avoid revealing the identity of subjects, and aggregating data across participants. The key linking names and study identification numbers will be kept separately from the data sets with limited access by study personnel. Only study personnel will have access to the data sets on protected servers. In order to maintain the highest standard of data entry quality, all data will be double-entered, with discrepancies highlighted so that they can be reviewed by the project coordinator. Oversight of all aspects of data management will occur with the PIs.

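### The only entry rule for the AE case report form is narrower than the plan's own AE collection, so AE counts taken from the form are at risk of being too low

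*Combined protocol and SAP*

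**What the plan says.** Section 5.4.5 (Reportable Adverse Events) first defines a serious adverse event and then gives one sentence on ordinary events. Its condition is "If clinically important and unexpected adverse experiences, or clinically important study-related adverse experiences occur"; the second limb with its consequence reads "clinically important study-related adverse experiences occur, they will be recorded on the adverse event case report form". Clinical importance is not defined there or elsewhere, and no other section gives a rule for entry on this form.

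Other sections describe wider collection:

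- Synopsis, Study Design: "The study aims to assess the safety and feasibility of oral nitrite in adults with HFrEF, HFpEF or healthy control".
- Section 5.4.1: "study staff will immediately report all adverse and serious adverse events to one of the PIs", with no filter on importance, expectedness or relatedness.
- Section 5.4.3: the severity scale begins at "Grade 1 (Mild): asymptomatic or mild symptoms; clinical or diagnostic observation only; intervention not indicated".
- Section 2.2.4: "Subjects will be contacted by phone weekly and this will include symptom review, assessing adverse events, interval histories and medication compliance".
- Section 2.2: "subjects will be asked to remain diligent in recording the time of study drug dosing and any associated symptoms".
- Table 1: AE assessment is marked at Visit 3, the four treatment-period calls, Visits 4 and 5, and the follow-up call.

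Section 2.1 describes the study as open-label and non-randomized. Sections 2.4 (endpoints) and 2.5 (analysis) contain no AE endpoint and no AE summary.

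**The concern.** The plan looks for adverse events widely and grades them from the mildest level, but the one sentence that sends them to a data form applies a filter. The filter rests on three judgements (importance, expectedness, relatedness), all made by people who know that the subject is on nitrite. The first of them has no definition.

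The events most exposed to the filter matter in this trial. Section 2.2.2 explains the stratified starting dose by low pressures or symptoms in the first three heart failure subjects, and describes the control experience by one asymptomatic systolic fall. Section 2.2.6 makes lightheadedness and dizziness the trigger for a possible change of dose or withdrawal. An event of this kind could be judged not clinically important and left off the form without any departure from section 5.4.5.

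AE data are also put to use. Section 5.4.4 has the investigator review them to reassess benefit and risk, and section 5.4.6 calls for a summary report to the regulatory agencies. If the form is the source, AE frequencies by group and dose would be incomplete in a way that the form itself would not show.

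**Working it through.** The plan states no AE rate or AE count to reproduce, so the check is one of logic, followed by illustrations of size.

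**Step 1. The rule as logic.** Let I = clinically important, U = unexpected, R = study-related. Section 5.4.5 requires entry when (I and U) or (I and R), that is, I and (U or R).

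| I | U | R | Entry required? |
|---|---|---|---|
| yes | yes | yes | yes |
| yes | yes | no | yes |
| yes | no | yes | yes |
| yes | no | no | no |
| no | yes | yes | no |
| no | yes | no | no |
| no | no | yes | no |
| no | no | no | no |

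Three of the eight combinations must be entered and five need not be. The five are all four combinations judged not important, plus the important event that is both expected and unrelated. The SAE definition earlier in the same section does not catch that last one, because it too requires the investigator to think the event study-related.

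**Step 2. Against the other sections.**

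- Section 5.4.1 covers all eight combinations, but its step is a report to a PI, not entry on a form.
- Section 5.4.3 supplies a grade for asymptomatic events needing no intervention. Many of these could plausibly fall in the four not-important rows, although Grade 1 and not important are not the same thing.
- Table 1 gives 1 (Visit 3) + 4 (calls) + 1 (Visit 4) + 1 (Visit 5) + 1 (follow-up call) = 8 AE assessments per subject, or 8 × 30 = 240 if all 30 subjects complete. None carries the section 5.4.5 filter.
- Diaries (sections 2.2 and 2.2.5), weekly calls (section 2.2.4) and the quarter-hourly readings over two hours after the first dose (section 2.3.1, Visit 3) can all hold events in source. No section says that findings from them go to the AE form.

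**Step 3. Size.** An under-count needs two figures that the documents do not give: the share of subjects with any AE, and the share of those who keep at least one event after the filter. By assumption only, take 30% to 50% for the first and 25% to 75% for the second, with n = 30:

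- 30%: 30 × 0.30 = 9 subjects with an AE; the form shows 9 × 0.25 = 2.25 to 9 × 0.75 = 6.75.
- 50%: 30 × 0.50 = 15 subjects; the form shows 15 × 0.25 = 3.75 to 15 × 0.75 = 11.25.

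These ranges show how the result depends on the assumptions. They do not estimate anything in this trial.

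**Step 4. A single event in a group of 10.** Sections 2.2.2 and 5.1.1 report one asymptomatic systolic fall among 10 controls. If entered, the form gives 1/10 with exact 95% interval 0.3% to 45% (lower limit 1 − 0.975^(1/10) = 0.0025; upper limit solves (1 − p)^10 + 10p(1 − p)^9 = 0.025, p = 0.445). If judged not important, it gives 0/10 with upper limit 1 − 0.025^(1/10) = 0.31. The documents do not say whether this event was entered, so the second case is hypothetical. The intervals overlap heavily and do not measure a bias.

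**The case against.** The strongest reply is that section 5.4.5 says what must be entered, not that nothing else may be. The sentence stands under a heading on reportable events, next to the reporting timeline, so it can be read as a minimum. The form itself is not in the documents. Reporting to a PI and entry on a form are different steps, so sections 5.4.1 and 5.4.5 do not strictly contradict each other. Events are also sought in many other ways, and the asymptomatic fall in one control was noticed and written into the protocol. This much stands: the conflict is an unreconciled difference between sections, and much of the information probably exists in source.

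It does not remove the point. The sentence is the only entry rule, so a site that follows it to the letter complies while leaving mild events off. Source capture makes the repair easy, but it does not give a complete AE dataset.

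Two stronger readings are tempting, and the documents do not support them. A reader might infer that mild, expected or unrelated events are never recorded. Step 1 shows otherwise: an important expected event is entered if it is study-related, as drug-related hypotension in heart failure would be, and an important unrelated event is entered if it is unexpected. A mild event may still be judged important, and absence from one form is not absence from all records. A reader might also infer that the safety result is biased low. The plan defines no AE analysis and does not name the source for one, so the downward direction is a risk and not an established result.

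**Conclusion.** The concern holds as an unreconciled and too narrow entry rule. Read literally, section 5.4.5 allows five of eight kinds of event to be left off the AE form. The decision turns mainly on an undefined judgement of importance, in an open-label study that names safety as an aim. If AE counts are taken from that form, they are at risk of being too low.

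The conclusion rests on two assumptions: that staff apply the sentence as written, and that the form feeds whatever AE summary is produced. The documents confirm neither. The size of any shortfall cannot be computed from them, and they do not show that any event has in fact been missed. The bioenergetic, functional and quality-of-life endpoints are not affected.

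**What to change.** Replace the last sentence of section 5.4.5 with: *Every adverse event found at any AE assessment in Table 1 is recorded on the AE CRF with grade (5.4.3), clinical importance, relatedness, expectedness and current dose.*

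Importance, relatedness and expectedness then become recorded attributes. They are used only to decide expedited reporting and no longer decide whether an event is recorded. For subjects already treated, check diaries, call notes, visit records and first-dose monitoring against the form, and enter any event found missing.

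The cost is one sentence in the protocol, slightly more data entry for 30 subjects, and a one-off source check. No dose or clinical management rule changes.
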